PROCOVAXED Trial Workflow on Intervention Blocks

Introduction to ED Staff: Clinical Research Coordinators (CRCs) will set up their workstation in the ED and introduce themselves to ED staff (nurses, physicians and mid-levels), informing them that they will be doing the PROCOVAXED study that day.

They will avoid telling providers intervention vs non-intervention arms.

Initial Screening and Scripted Consent for Surveys: CRCs will review ED dashboards for inclusion and exclusion information. When an eligible patient is identified, the CRC will ask the nurse or doctor caring for the patient whether it is Ok for them to approach the patient about the first survey. Whenever possible, the CRC will ask the provider to first ask the patient if they may speak to them.

For provider approved patients: CRCs will approach eligible patients and deliver a scripted consent for two short surveys (Pre-intervention) FIRST SURVEY and the (Post-Intervention) SECOND SURVEY. See Scripted Consent for the Intervention periods.

Complete PROCOVAXED Screening. Enrollment log for all patients.

First Survey in the ED: For patients agreeing to the above surveys, we will administer a short survey – a baseline survey to be complete after obtaining scripted consent at the beginning of their ED visit (before exposure to the messaging platform intervention – PROCOVAXED FIRST SURVEY). CRCs will have the option of inputting survey responses to REDCap on iPads in real time or using paper surveys (and later inputting into REDCap). **These surveys are to be delivered orally (CRC asks questions), not via handing them out.**

Covid Vaccine Flyer, Videos and Telling Provider to Deliver Message: At the end of the survey, the CRC will deliver the Covid vaccine information flyer and ask the patient if they will watch a short video about Covid vaccines. If they agree to watch the video, the CRC will show them the video on the iPad. After finishing with the video, the CRC will tell the subject that they will be back in about an hour for the second survey. The CRC will then leave the room and tell the patient's primary provider (doctor, mid-level practitioner, or nurse) to deliver the message (hand them the scripted message).

Intervention: The intervention will consist of three messaging platforms to reduce vaccine hesitancy that have been produced in Specific Aims I and II:

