- Video clips – short (approximately 3 minute) Public Service Announcement type videos that we developed during Specific Aims I and II. These will be shown to the subjects on iPads.
- Printed materials – one page information sheets.
- Face to face messaging – short (< 1 minute), scripted message from the patient's providers in the ED (nurse or provider)

All of the above platforms have been reviewed and approved by the UCSF IRB

Each site will maintain a library of

A. 4-5 versions of the video clips - the particular version used in any particular patient

will be tailored to particular patients as guided by our previously conducted qualitative data analysis in Specific Aim I. See ***below

B. 4-5 versions of printed materials – likewise, particular versions will be tailored to particular patients. See ***below

C. 1 version of the scripted message

Delivery of Study Intervention: All surveys and interventions will be delivered in real-time patient visits in site EDs, during waiting times such that they will not interfere with patient care.

- Video clips will be delivered by iPads in patient's rooms.
- Printed materials will be handed to subjects by CRCs.
- CRCs will hand the patient's provider(s) the script for face-to-face messages and ask that they deliver it to the patient. These messages will be very short and should not significantly impact provider workflow. Notably, vaccine messaging is recommended in the ED by the American College of Emergency Physicians and other health care organizations (Centers for Disease Control).

***We will deliver messaging from our platform libraries in patients' preferred language (English, Spanish). To the extent possible, we will follow qualitative interview recommendations from Specific Aim 1 to choose platforms from site libraries that match video clip and printed material messengers with subjects' likely preferences for race, ethnicity, age and gender (e.g., Latino messenger on video clip with Latino subject).

At months 4 and 8 of the trial, we will review subject feedback regarding the most effective and least effective messaging tools and will consider modifying the choices and matching of messaging platforms, e.g., greater emphasis on video clips over printed materials. These changes will not entail true alterations in the overall PROCOVAXED intervention strategy; they will instead be minor adjustments to platform content.

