Second Survey (Post-Intervention) in the ED: We will administer a short survey approximately one hour after the intervention (after all 3 platforms). See SECOND SURVEY: INTERVENTION GROUP.

Complete Master Data Flow Log after each patient enrolled.

NOTE: All of the above study procedures should be performed in patient waiting times and not interfere or disrupt patient care in any way.

-

Study Procedures: Non-Intervention Blocks

The anticipated flow of the study during **Non-Intervention Blocks** is summarized in Figure 1.

Figure 2: Non-Intervention Blocks Study Flow

PROCOVAXED Trial Workflow on Non-Intervention Blocks

Introduction to ED Staff: Clinical Research Coordinators (CRCs) will set up their workstation in the ED and introduce themselves to ED staff (nurses, physicians and mid-levels), informing them that they will be doing the PROCOVAXED study that day.

CRCs will avoid telling providers intervention vs non-intervention arms.

Initial Screening and Scripted Consent for Surveys: CRCs will review ED dashboards for inclusion and exclusion information. When an eligible patient is identified, the CRC will ask the nurse or doctor caring for the patient whether it is Ok for them to approach the patient about the first survey. Whenever possible, the CRC will ask the provider to first ask the patient if they may speak to them.

For provider approved patients: CRCs will approach eligible patients and deliver a scripted consent for two short surveys: the Non-Intervention FIRST SURVEY and the Non-Intervention SECOND SURVEY. See Scripted Consent for the Non-Intervention periods.

CRCs will complete screening and enrollment log indicating whether or not they agreed to this survey. If they agreed to survey, CRC will assign a Study ID# and proceed to Master Data Flow form.

First Survey in the ED: For patients agreeing to the above surveys, we will administer a short survey – a baseline survey to be complete after obtaining scripted consent at the beginning of their ED visit (before exposure to the messaging platform intervention – PROCOVAXED FIRST SURVEY). CRCs will have the option of inputting surveys to REDCap on iPads in real time or using paper surveys (and later inputting into REDCap).

These surveys are to be delivered orally (CRC asks questions), not via handing them out. First Surveys are the same for intervention and non-intervention blocks.

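### In intervention weeks the script hand-over reveals the arm to providers, who then decide, with no stated criterion, which later patients may be approached

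*Combined protocol and SAP*

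**What the plan says.** All references are to the combined protocol and SAP.

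- **Masking intention.** Under Introduction to ED Staff, the Intervention Blocks section states "They will avoid telling providers intervention vs non-intervention arms" and the Non-Intervention Blocks section states "CRCs will avoid telling providers intervention vs non-intervention arms".
- **Hand-over.** In intervention weeks, after the video, the CRC tells the patient's primary provider "to deliver the message (hand them the scripted message"). The paragraph on delivery of the intervention repeats that providers are given "the script for face-to-face messages and ask that they deliver it to the patient". The control workflow has no such step.
- **Permission to approach.** In both workflows, "the CRC will ask the nurse or doctor caring for the patient whether it is Ok for them to approach the patient". Only those who pass go on: "For provider approved patients: CRCs will approach eligible patients and deliver a scripted consent for two short surveys". Neither workflow says on what grounds a provider may decline.
- **Recruitment.** The Recruitment section plans to approach every eligible adult in the daily six-hour window and lists the exclusions, which are read from triage information.
- **Randomization.** The arm is fixed for a whole week at a site. The only masking measure in this section limits how early a site learns the next week's assignment.
- **Analysis.** The Primary Analysis covers ED patients who were surveyed.

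**The concern.** The masking instruction and the hand-over cannot both hold for a provider who has received a script. Because the arm does not change within a site-week, one hand-over tells that provider the arm for every later patient that week. That provider may then be asked whether the next patient can be approached. Nothing in the text separates the person giving permission from the person delivering the script.

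Randomising weeks balances the patients who arrive. It does not balance those who are let through once the arm is known. A patient whom a provider holds back is never consented or surveyed, and intention-to-treat analysis cannot recover someone who was never enrolled. The primary model has terms for assignment, centre and secular trend and lists no patient-level covariates that might offset a difference in case mix. If providers who know the arm refuse differently, and the patients they refuse differ in willingness to be vaccinated, the arms differ before the first survey.

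**Working it through.** **1. The plan's own figure.** The Sample Size section gives 15% versus 22%, alpha 0.05, power at least 0.9 and 645 per arm. With the two-sided pooled formula:

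n = [1.960·√(2·0.185·0.815) + 1.282·√(0.15·0.85 + 0.22·0.78)]² / 0.07² = (1.076 + 0.701)² / 0.0049 ≈ 645 per arm, 1,290 in total.

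This matches and is not in dispute. It supplies the 15% base rate and the 7-point yardstick.

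**2. Who knows the arm, and when.**

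| Step | Intervention week | Control week |
|---|---|---|
| CRC avoids announcing the arm | yes | yes |
| Provider asked for permission to approach | yes | yes |
| Provider asked, where possible, to speak to the patient first | yes | yes |
| Provider handed a script | yes | no |

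Only the last row differs. It reveals the arm directly in intervention weeks. In control weeks the arm can only be inferred from the absence of a script. Unmasking therefore builds up over the week as more providers receive scripts.

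**3. Size if every intervention-week approach meets an unmasked provider.** The documents give no refusal rates, so these are assumptions. Let l be the share held back and a the acceptance rate among those held back, with 15% acceptance among all eligible patients and no true effect.

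Observed rate = (0.15 − l·a)/(1 − l), so the false difference = (0.15 − a)·[l₁/(1 − l₁) − l₀/(1 − l₀)], with l₁ for intervention weeks and l₀ for control weeks.

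- a = 0.05, l₀ = 0.05, l₁ = 0.15: 15.53% versus 16.76%, a difference of 0.10·(0.1765 − 0.0526) = 1.24 points, or 18% of the 7-point target. At 645 per arm, ignoring clustering, the chance of a falsely significant benefit is roughly 9% instead of 2.5%.
- a = 0.05, l₀ = 0.10, l₁ = 0.20: 16.11% versus 17.50%, a difference of 1.39 points.
- l₀ = l₁: zero.

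**4. Size if unmasking is partial.** The plan expects at least one enrolment per site per day; 1,290/5/50 = 5.16 per site-week. Take 5 a week and assume the provider asked is drawn at random from m providers, with no word of mouth. The share of approaches that meet a provider who already holds a script is s = (1/5)·Σ[1 − (1 − 1/m)^k], for k = 0 to 4. Applying the extra 10-point refusal only to that share gives l₁ = 0.05 + 0.10·s.

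| m | s | l₁ | False difference (a = 0.05) |
|---|---|---|---|
| 5 | 33% | 0.083 | 0.4 points |
| 10 | 18% | 0.068 | 0.2 points |
| 20 | 10% | 0.060 | 0.1 points |

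Faster enrolment, or providers talking to each other, moves these back towards 1.24.

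**5. Direction.** The sign is that of (0.15 − a). If refusals are unrelated to acceptance (a = 0.15), the bias is zero even when refusal rates differ. If likely acceptors are held back (a = 0.25, same refusal rates), it is −0.10·0.1238, or −1.24 points. Bias against the intervention costs power: if the true rate is 22% and 10% of would-be acceptors are declined in intervention weeks, the observed rate is 0.198/(0.198 + 0.78) = 20.2%, and power falls from 90% to 70%.

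**The case against.** The best defence is that provider delivery is one of the three intervention components, so the provider who delivers it must know the arm. The text says CRCs avoid telling, not that providers are blinded; the only role described as blinded is the one-month follow-up CRC. Not announcing the arm still limits what other staff know. The permission question is worded identically in both workflows. The script takes under a minute. In EDs seeing 150 to 250 patients a day, with about five enrolments a week, many approaches may meet a provider who has had no script. All of this stands, and it limits the size of the problem. It does not reconcile the instruction with the hand-over or supply a criterion for refusal.

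A reader might go further in several ways that the documents do not support:

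- **That approval is free in control weeks.** The control workflow also asks providers, where possible, to speak to the patient first.
- **That providers decide eligibility.** The CRC screens first; the provider grants permission.
- **That refusals go unrecorded.** The fields listed under Data Recording cover approached patients and omit provider refusal, but a screening and enrolment log is kept for all patients and its contents are not shown.
- **That the Aim IV comparison is presented as provider-masked.** No section says so.
- **That bias in favour of the intervention is shown.** Only a route is shown.

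The CRC who recruits also knows the arm, through the arm-specific consent scripts. The fix below does not change that.

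**Conclusion.** The point holds as a limited one. The masking instruction fails for any provider who has received a script, and those providers hold an open veto over who is approached for the rest of the week. That veto also sits badly with the plan to approach all eligible patients. The result is a possible route to differential selection into the analysed set, and it widens as scripts are handed out.

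The size and direction are unknown. The 1.2-point figure rests on assumed refusal rates, an assumed 5% acceptance among those held back, and every intervention-week approach meeting an unmasked provider. It is upper-end in that last respect, not a bound on how selective refusal could be. Under partial unmasking the same assumptions give about 0.1 to 0.4 points, and other assumptions give zero or a negative value. The point is worth correcting because the remedy is cheap and the effect could not otherwise be ruled out; it does not undermine the weekly cluster design.

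**What to change.** 1. In both workflow sections, state that providers are unmasked once they receive a script. The instruction not to announce the arm can stay for other staff.
2. Keep the permission question identical in both arms, but limit refusal to an exclusion already listed under Recruitment or a clinical reason not to approach now. All other eligible patients are approached.
3. Record each provider refusal and its reason in the existing screening log, if it does not already do so.
4. Report by arm the provider refusals with reasons, the approach and enrolment rates, and the FIRST SURVEY characteristics.

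The cost is a wording change, at most one log field, and some loss of provider discretion. Randomisation and sample size are untouched. The permission step remains unmasked, so these changes limit selection and make it visible; they do not remove it.

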Second Survey in the ED: We will administer a second short survey at some time (approximately 1 hour) after the FIRST SURVEY. See SECOND SURVEY: NON-INTERVENTION GROUP. These second surveys in the non-intervention group have the same key primary and secondary outcome questions as in the INTERVENTION GROUP second surveys. SECOND SURVEY: NON-INTERVENTION GROUP.

NOTE: All of the above study procedures should be performed in patient waiting times and not interfere or disrupt patient care in any way.

- **Research Staff Informing of ED Providers when Participants will accept Covid vaccine**

At this time all of our EDs have the capability of administering COVID19 vaccines in some manner, and we expect that this will continue for at least the first 6 months of the trial. The last question in the SECOND SURVEY **in both arms** of the study is “Would you accept the Covid vaccine in the emergency department today if your doctor asked

you?" When a participant says they will accept the vaccine, the CRC or research staff will ask the patient if they can notify the patient's providers (nurse and/or physician) that they said they will accept the vaccine. They will also ask the patient if they (the CRC) can check to see if the patient receives the vaccine in the ED.

Other than this question and notification, research staff will not push that they get vaccinated.

- **Consent for 1- Month Follow Up Surveys for patients saying No to Vaccine in ED**

For all patients saying **no** to the question "*Would you accept the Covid vaccine in the emergency department today if your doctor asked you?*", research staff will ask if they can contact them and review their records in a month for follow up via full written consent. If patient says yes, then the CRC will get full **written** informed consent, including a separate HIPAA form, for review of their records and phone call. See FOLLOW UP Consent. Patients will not be compensated for participation. We will then ask Subjects for their best phone number(s) to reach them for a follow-up phone call. Sites will maintain a separate password protected database of subject IDs and follow up phone #s. Patients may agree to a phone call and not the EHR review, or vice versa. In those cases obtain the relevant consent, and note that they have accepted only one or the other.

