We will also ask for 1-month follow up in those subjects who said YES to accepting the Covid vaccine in the ED and did not get the vaccine in the ED. We will attempt to get full **written** informed consent for review of their records and phone call at 1 month in the same manner as above.

- **Community Covid Vaccine Information for patients saying No to Vaccine in ED**

Additionally, if the patient says no to accepting the vaccine in the ED today, the CRC will also ask, "*Would you like some information about where you can get a Covid vaccine outside of the emergency department?*" If the patient says yes, then the CRC will provide information about where they can get a Covid vaccine outside of the ED (community locations).

- **Primary Outcomes and Ascertainment**

Our primary outcome for Specific Aim III is **vaccine acceptance at the time of SECOND SURVEY** (the converse of vaccine hesitancy) defined as a response of "yes" to the question "*Would you accept the Covid vaccine in the emergency department today if your doctor asked you?*" This and other outcomes for Specific Aim III will be ascertained during the SECOND SURVEYS at the end of their index ED visit. **If the patient says yes, the CRC will then ask the patient if it is acceptable for them to notify the provider and confirm their receipt of the vaccine.** If the patient says yes, the CRC will notify the provider that they are willing to get the vaccine. CRCs will later confirm with the provider that the patient received the COVID-19 vaccine in the ED.

Our primary outcome for specific aim IV will be **uptake (receipt) of a COVID-19**

vaccine (at any vaccination location) within 28 to 32 days after their index ED visit. For ascertainment of this primary outcome:

- As above, for patients who stated they would accept it in the ED today, CRCs will confirm whether the patient received the vaccine directly from providers or by review of that patient's EHR the following day.
- For those who do not accept the vaccine in the ED **and consent to follow up:** We will conduct EHR review and follow-up phone calls (*Have you received a COVID-19 vaccine?*) one month after index ED visits.

- **28 to 32 Day Follow-Up for Ascertainment of Primary Outcomes**

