result in greater acceptance and uptake of the COVID-19 vaccine. Following the recommendations of Hussey and Hughes, our statistical analyses of AIMS III and IV will focus on comparing the vaccine and uptake rates during the time periods when PROCOVAXED is in place (intervention) and when the system is not in place (usual care) using mixed effects logistic models.^{122,123} The outcomes of interest are the binary indicators of whether a patient will accept the COVID-19 vaccine ("Will you accept the COVID-19 vaccine if it was offered to you" – yes/no) and whether they have received a COVID-19 vaccine (uptake - yes/no) upon follow-up. Models will include a random center effect to accommodate potential within-center characteristics (e.g., case mix, demographics), as well as terms for time and intervention. Hypothesis tests will focus on the statistical significance of the intervention indicator. We will fit the mixed effects models using maximum likelihood and routines in Stata or SAS.

We will test our primary hypothesis and analyze outcomes according to the study arm (index visit in intervention month vs non-intervention month) to which patients were allocated, regardless of whether they received PROCOVAXED messaging or not - **intention to treat analysis**. We will also conduct a **per-protocol analysis**, in which we assess results that would occur if they actually did or did not receive PROCOVAXED messaging (e.g., viewed the video clip given to them) during their index visit (ascertained by direct questioning in the Outcome Survey). When compared to the primary analysis, the per-protocol analysis will allow us to dissect the reasons for success (or failure) in demonstrating improved vaccine acceptance and uptake with PROCOVAXED. For example, if we find better acceptance and uptake in the per protocol analysis and not in the intention to treat allocation analysis, we would subsequently seek ways to improve delivery of PROCOVAXED messaging. Conversely, if both analyses fail to improve acceptance, then the PROCOVAXED intervention truly fails and other efforts to improve delivery would not be indicated. In addition to the effects on *total* vaccine acceptance, we will also examine the effect of PROCOVAXED on acceptance in patient sub-groups, especially African Americans and Latinos. PROCOVAXED may work for one patient sub-group and not others - these additional analyses will guide future directions and modifications of PROCOVAXED messaging.

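### The primary acceptance item closes arm-specific Second Survey forms, and the plan does not rule out that only intervention patients are asked about the messaging just before it

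*Combined protocol and SAP*

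**What the plan says.** The protocol names two Second Survey forms. Section IX (Intervention Blocks) directs staff to one: "See SECOND SURVEY: INTERVENTION GROUP". Section X (Non-Intervention Blocks) directs them to the other: "See SECOND SURVEY: NON-INTERVENTION GROUP". On what the forms have in common, section X says: "These second surveys in the non-intervention group have the same key primary and secondary outcome questions as in the INTERVENTION GROUP second surveys". For the baseline survey the statement is broader: "First Surveys are the same for intervention and non-intervention blocks".

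Section XI places the acceptance question as "The last question in the SECOND SURVEY", and the sentence goes on to say that this holds in both arms. Section XIV makes a yes to that question the Aim III primary outcome and adds: "This and other outcomes for Specific Aim III will be ascertained during the SECOND SURVEYS at the end of their index ED visit".

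Two other places call for information about the messaging from patients. The per-protocol analysis in section XVI needs to know whether a patient received it (for example, watched the video), which is to be "ascertained by direct questioning in the Outcome Survey". Section IX says that at months 4 and 8 "we will review subject feedback regarding the most effective and least effective messaging tools". The term Outcome Survey is not defined, and no form is named for the feedback.

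**The concern.** An item asked last is answered in the context of everything asked before it. If the intervention form asks patients whether they saw the video or flyer, or which tool worked best, those patients are made to recall the messages immediately before the primary question. If the control form has no counterpart, the lead-in to the primary item differs by arm.

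Any effect of that lead-in would coincide with allocation. Neither the intention-to-treat analysis nor the mixed logistic model could separate it from the effect of the messaging, and a blinded interviewer would not remove it. It would also be absent from the real-world implementation that section XVI gives as the target, because patients outside a trial are not surveyed. A yes also leads, with the patient's permission, to provider notification, so a shifted answer could carry into Aim IV uptake.

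**Working it through.** **Step 1. Which survey is the Outcome Survey?** The protocol describes three contacts at which patients are questioned.

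- *First Survey.* It is given before exposure and is the same in both arms, so it cannot ask about receipt of messaging.
- *One-month follow-up.* The caller is to be blinded to study group, which questions about the messages would defeat. It reaches only patients who give written consent, and it is sought only from those who decline the vaccine or who accept but are not vaccinated in the department. It fits poorly.
- *Second Survey.* It follows the intervention, has arm-specific forms and carries the Aim III outcomes. It is the only good fit.

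The feedback on messaging tools must also come from exposed patients, so the Second Survey is a likely home for it, but here the text gives no form at all.

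**Step 2. What follows about order?** If messaging questions are on the intervention form and the acceptance item is last, they precede it. Whether controls are asked parallel questions is not stated.

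**Step 3. The plan's own figure.** Inputs from section XVIII: control rate 15%, intervention rate 22% (an increase of 7 points), alpha 0.05, power 0.90, individual-randomization formula. Sidedness is not stated; two-sided reproduces the figure. With mean proportion 0.185:

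n per arm = [1.960 × √(2 × 0.185 × 0.815) + 1.282 × √(0.15 × 0.85 + 0.22 × 0.78)]² / 0.07²
= [1.960 × √0.30155 + 1.282 × √0.29910]² / 0.0049
= (1.0763 + 0.7009)² / 0.0049 = 644.6, rounded up to 645.

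The total is 1,290, as stated. Power at 645 per arm is 0.900.

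**Step 4. Scale of an upward shift with no true effect.** The documents give no size for an order effect, so shifts of 1 to 3 points are assumed. Let d be the shift, p₁ = 0.15 and p₂ = 0.15 + d, with se₀ the pooled and se₁ the unpooled standard error at 645 per arm. The chance of a significant two-sided result is

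1 − Φ[(1.960 se₀ − d)/se₁] + Φ[(−1.960 se₀ − d)/se₁].

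| Shift | Extra yes answers (645 × d) | se₀ | se₁ | Upper tail | Two-sided |
|---|---|---|---|---|---|
| 0 | 0 | 0.01988 | 0.01988 | 2.5% | 5.0% |
| 1 point | 6 | 0.02015 | 0.02015 | 7.2% | 7.9% |
| 2 points | 13 | 0.02041 | 0.02041 | 16.3% | 16.5% |
| 3 points | 19 | 0.02067 | 0.02065 | 30.5% | 30.6% |

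**Step 5. Scale of a downward shift against a true 7-point effect.** The same formula with p₂ = 0.22 − d:

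| Shift | Intervention rate observed | Power |
|---|---|---|
| 0 | 22% | 90.0% |
| −1 point | 21% | 80.2% |
| −2 points | 20% | 65.7% |
| −3 points | 19% | 48.1% |

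Both tables treat patients as independent and ignore clustering.

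**The case against.** A reader might infer that intervention patients are in fact questioned about the messaging before the primary item and controls are not, so that the instrument is unequal between arms. The documents do not support that as a statement of fact.

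- Neither form is reproduced, and the Outcome Survey is undefined.
- Section XV describes another record of exposure: research staff log whether the messaging platforms were delivered.
- The per-protocol text speaks of patients who did or did not receive messaging, which leaves room for asking controls the same questions.
- Section X says that the key outcome questions are the same. It does not say that nothing else is shared.
- Sections XI and XIV give the acceptance item one wording and one position for both arms.

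All of this stands, and it makes the point conditional. It does not remove it: direct questioning about receipt is planned, and the Second Survey is the only described survey that suits it.

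The magnitudes can also be attacked. Three points is 43% of the 7-point target (3/7), a large share to assign to question order in patients who had the flyer, video and provider script about an hour before. The calculations would apply to any bias of that size and are not evidence that this one exists. That also stands.

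Finally, the last position has a purpose: the answer leads to provider notification, follow-up consent or community information. Patients who have already said yes or no may also report exposure differently, which touches the per-protocol analysis. These are real but small costs, and they fall on secondary uses of the survey.

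**Conclusion.** The point holds in conditional form. The plan does not show that the questions preceding the primary item are the same in both arms, and its own description suggests that they are not. This rests on two assumptions: that the Outcome Survey is the Second Survey (a strong inference), and that controls are not given parallel messaging questions (not stated either way). That the feedback items are collected there too is possible, but less well supported.

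The size and direction of any effect are unknown. The 5% to about 8–31% range for false significance and the 90% to about 80–48% range for power show only that a shift of 1 to 3 points in either direction would matter to the primary test. It would be wrong to read them as an estimate of bias, or to conclude that the trial's error rate is inflated. The sample size of 1,290 is unaffected.

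The change is still worth making: it protects the primary outcome at little cost and does not depend on settling the size of the effect.

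**What to change.** In both arms, ask and record the acceptance item before any question on receipt of, or feedback on, the messaging. Shared outcome questions may stay ahead of it if they come in the same order on both forms. Keep provider notification, community vaccine information and follow-up consent at the end of the survey, as now. Amend section XI, which calls the item the last question, to match.

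State in the protocol which survey the Outcome Survey is, which form collects the messaging feedback, and whether controls are asked parallel questions. If no messaging question precedes the item on either form, saying so settles the point.

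The cost is a reordering of two forms and their REDCap screens, with no added questions, staff or patients. Exposure and feedback items would then be answered after the acceptance answer, which should be noted when the per-protocol results are interpreted. If enrolment has begun, the change needs IRB review, a logged date, introduction in both arms at all sites at the same time, and a sensitivity check comparing the treatment effect before and after it.
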